4.4.3.3 HFMS

The HFMS has been removed from the schedule of assessments as of protocol version 3. The change from baseline in the HFMS score and the absolute value at each available assessment visit will be summarized using descriptive statistics.

HFMS assessments will be subject to the same missing data rules defined for the MFM score in Section 4.4.1.1.

4.4.4 Sensitivity Analyses

Some patients may perform MFM assessments within a certain time period after having surgery to treat scoliosis or suffering a bone fracture that would not be representative of their true ability. If this occurs for more than 10% of the ITT population, the change from baseline in the MFM D1+D2 score and the absolute value at each visit will be summarized using descriptive statistics with the following rules:

- No imputation for missing MFM scores will be applied.
- Following the death of a patient, MFM scores will be set to missing.
- If an individual MFM item is missing or was 'Not done,' the item will be set to zero in accordance with the MFM user manual.
- If a patient performs the MFM-20 instead of the MFM-32 at any post-baseline visit, the assessment will be set to missing.
- In case of a MedDRA preferred term (PT) of 'scoliosis surgery,' 'spinal fusion surgery,' 'spinal cord deformity correction' or 'arthrodesis' (spinal arthrodesis) all motor function scores up to 2 years after the surgery will be set to missing.
- In case of a PT of 'spinal rod insertion' or 'spinal rod removal' (growing rod instrumentation or adaptation) all motor function scores up to 4 months after the event will be set to missing.
- In case of a high level term (HLT) of 'limb fractures' or 'spinal column fractures,' all motor function scores up to 4 months after the event will be set to missing.

These rules will also be applied for events that occurred before the start of the study (including events reported for the historical data collection part of the study).

4.4.5 Subgroup Analyses

Mean changes from baseline in the MFM D1+D2 score at each visit and corresponding 95% CIs will be presented graphically for subgroups as follows:

- Age: 6-15, \geq 16 years old
- SMA type: Type 2, Type 3
- SMN2 copy number
- Sex
- Country

4.5 PHARMACOKINETIC AND PHARMACODYNAMIC ANALYSES

Pharmacokinetic and pharmacodynamic analyses will be presented in a separate report.

4.6 SAFETY ANALYSES

All safety variables will be summarized using descriptive statistics. Analyses will be based on the safety population.

Post-baseline safety assessments, including assessments performed at an unscheduled visit or at an early discontinuation visit, will be assigned to a scheduled study visit based on the following time windows:

Visit	Study Day	Time Window (in Study Days)
V2 (Week 13)	92	Day 2 – Day 137
V3 (Week 26)	183	Day 138 – Day 228
V4 (Week 39)	274	Day 229 – Day 319
V5 (Week 52)	365	Day 320 – Day 456
V6 (Week 78)	547	Day 457 – Day 638
V7 (Week 104)	729	Day 639 – Day 820
V8 (Week 130)	911	Day 821 – Day 1002
V9 (Week 156)	1093	Day 1003 – Day 1184
V10 (Week 182)	1275	Day 1185 – Day 1366
V11 (Week 208)	1457	Day 1367 – Day 1548
...		

These time windows will be used for all parameters, including those that were not scheduled to be collected at that visit. If multiple valid values for a variable are recorded in the same time window, the record closest to the scheduled study visit will be selected for summary of the data.

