##### **Procedure for Dose Increase**

*All patients are asked to attend an unscheduled dose increase visit as early as possible, to increase their dose to the recommended level. Patients will be required to re-consent prior to dose increase and related assessments. If the medical condition of a patient does not allow an additional study visit or the date of the next regular study visit is scheduled close to when Protocol BN29854, Version 4 becomes in effect, the option to increase the dose at the next scheduled study visit will be offered.*

*Dose increase visit procedure options:*

- 1. Patients attend an additional dose increase visit to increase their dose to the recommended level as early as possible. Only the specified assessments for the dose increase visit will be performed (see the Schedule of Assessments in [Appendix 1](#)).*
- 2. Patients attend their next scheduled regular visit to increase their dose to the recommended level. Specified assessments for the dose increase visit (see [Appendix 1](#)) and scheduled assessments for the regular visit will be performed.*

*Prior to the dose increase, specified assessments need to be performed (see Schedule of Assessments in [Appendix 1](#)). These assessments include 24-hour Holter ECG monitoring (see Section [4.4.9.1](#)) as well as blood sampling for PK and biomarker assessments (Section [4.4.8.1](#)). If a patient performs the procedure for dose increase as part of a regular study visit and an ECG assessment is scheduled for this visit, only the 24-hour Holter ECG needs to be performed. If PK and biomarker samples are scheduled for this regular study visit, the relevant sample types need to be collected only once.*

*Blood samples shall be taken predose. Therefore, before attending the dose increase visit, patients should be reminded not to take the drug at home, as they will have it administered with their next meal after the assessments are conducted.*

*Starting on the day after the removal of the Holter ECG monitor, patients will receive olesoxime at a dose of 10 mg/kg to be taken twice daily with breakfast and dinner.*

*In addition to the dose increase procedure, the investigator will fill out the OFS and the CGI-C. The OFS is a brief survey designed to explore potential benefit of olesoxime on fatigability (i.e., endurance). The CGI-C assesses the clinician-reported change in the patients overall health status.*

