#### **Dose Increase Safety Follow-Up Visit**

*Patients who have consented to receiving the 10 mg/kg dose BID will return for a dose increase safety follow-up visit 4 weeks after the dose increase. During this follow-up visit, patients will also be requested to have 24-hour Holter ECG monitoring and blood sampling for safety and PK assessments. Blood samples should be taken predose.*

*After the dose increase safety follow-up visit, patients will return to the site for their next visit at the next scheduled timepoint per protocol. In the case of an unscheduled dose increase visit, the next visit should not be delayed and should take place at the next scheduled visit per the protocol.*

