## **6.6 PRIMARY ANALYSES**

Safety analysis will be based on the safety population.

Safety variables (e.g., laboratory tests, vital signs, and ECG) will be summarized for each assessment time (including follow-up) using descriptive statistics. *The data will be summarized by the dose being taken at the time of the assessment (10 mg/kg QD or 10 mg/kg BID). Data from the two 24-hour Holter ECG assessments will also be summarized.*

Adverse events will be coded and summarized by body system and preferred term. Adverse events will also be summarized by intensity and relationship to trial treatment as assigned by the investigator. Serious adverse events will be summarized separately. *Adverse events will be summarized by the dose being taken at the onset date of the adverse event.*

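### The SAP was not aligned with protocol Version 4: it omits the by-dose and Holter safety summaries, and its closest-record rule usually leaves the 4-week post-increase laboratory sample out of the by-visit tables

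*SAP*

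**What the plan says.** **Protocol Version 4.** Section 6.6 says that safety variables "will be summarized for each assessment time (including follow-up) using descriptive statistics". It adds: "The data will be summarized by the dose being taken at the time of the assessment (10 mg/kg QD or 10 mg/kg BID". It also states "Data from the two 24-hour Holter ECG assessments will also be summarized" and "Adverse events will be summarized by the dose being taken at the onset date of the adverse event". Section 3.1.1.4 gives two routes to the higher dose. The default is an extra visit (Option 1): "All patients are asked to attend an unscheduled dose increase visit as early as possible". The alternative is to increase at the next regular visit (Option 2). Four weeks later there is a safety follow-up at which "patients will also be requested to have 24-hour Holter ECG monitoring and blood sampling for safety and PK assessments".

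**SAP.** Sections 2 and 3.1 describe 10 mg/kg once daily for everyone, and the latest protocol version mentioned anywhere is 3 (section 2.1.3). Section 2.3 nevertheless applies the SAP to the final analysis of everything collected to study end. Section 4.6 places post-baseline safety assessments, "including assessments performed at an unscheduled visit or at an early discontinuation visit", into windows around the regular visits. When a window holds more than one value, "the record closest to the scheduled study visit will be selected for summary of the data". Sections 4.6.2 (adverse events) and 4.6.4 (laboratory) have no split by dose, and section 4.6.6 covers standard ECGs only. Section 4.6.1 computes compliance as days under treatment divided by treatment duration.

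**The concern.** Safety is the primary objective, and the 4-week visit exists to check safety once the higher dose is expected to be at steady state. If the SAP is followed as written, the outputs that protocol 6.6 asks for on this question are not produced, and the window rule works against the new visit. A sample taken 4 weeks after the increase competes with a regular-visit sample that is due close to target, and it normally loses. For patients who increase at a regular visit, the value shown in that window is then usually the one drawn before the increase, on once-daily dosing. The group-level laboratory change from before to after the increase appears in no table.

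A smaller point concerns compliance. The formula counts days and has no rule for a day on which one of two doses was taken.

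**Working it through.** **Inputs.** SAP 4.6: window limits and targets. Protocol Appendix 1: regular visits ±14 days from Visit 6 on; follow-up 28 ± 5 days after the increase. The documents give no distribution of visit times, no split between Options 1 and 2, and no rate of missed visits. Anything that depends on these is an assumption.

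**1. The SAP's own windows.** Target day = 7 × week + 1, with boundaries halfway between targets. For Visit 7: 7 × 104 + 1 = 729; lower limit (547 + 729)/2 + 1 = 639; upper limit (729 + 911)/2 = 820. Width 820 − 639 + 1 = 182 days, from −90 to +91 around target. All ten listed windows (V2 to V11) are reproduced this way, rounding halves down.

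**2. Option 2 (increase at a regular visit).** Let the visit fall *v* days from target (−14 to 14) and the follow-up *v* + 28 + *e* days from target (*e* from −5 to 5). The follow-up is closer only if |*v* + 28 + *e*| < |*v*|, that is −*v* > (28 + *e*)/2, which is at least 11.5. So the visit must be 12, 13 or 14 days early.
- *v* = −14: 5 of 11 values of *e* qualify; *v* = −13: 3 of 11; *v* = −12: 1 of 11.
- With uniform timing: 9 of 29 × 11 = 319, or 2.8% selected and 97.2% left out. The SAP has no tie rule; giving the 3 ties to the follow-up makes 12/319, so 96.2% are left out.
- Example: visit on Day 729, follow-up on Day 757. Distances are 0 and 28, so the pre-increase sample is shown.

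**3. Option 1 (extra visit).** With the regular visit attended within 14 days of target, a follow-up more than 14 days from target cannot be selected. That leaves at most 2 × 14 + 1 = 29 of 182 days (15.9%).
- With uniform timing, a visit *v* days off target leaves 2|*v*| − 1 strictly closer days. Summed over *v* = ±1 to ±14 this is 2 × 14² = 392. Then 392/(29 × 182) = 392/5,278 = 7.4% selected and 92.6% left out.

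**4. Sensitivity.**
- Option 1: 100% left out if visits are on target; 87.6%, 82.7% and 77.7% if 10%, 20% and 30% of regular visits are missed; about 68% in the most favourable case tried.
- Option 2: 100% if no visit is more than 11 days early; 6/11 = 54.5% if every visit is 14 days early, or 45.5% if ties also go to the follow-up.

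**5. Selecting the closest record within dose.**
- Option 2: the follow-up is the first twice-daily sample and the next regular visit lies in the next window, so the loss is 0%.
- Option 1, visits on target: an increase 1 to 63 days after a visit puts the follow-up in that visit's window (63 + 28 = 91), where it is the only twice-daily value. For the other 118 of 181 days it competes with a twice-daily regular visit and loses: 65.2%. Across the timing assumptions tried, the loss is about 15% to 65%.

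**6. Compliance.** If one of two doses is taken every day, 50% of prescribed doses are taken. If a day with any dose counts as under treatment, the SAP formula gives 100%. Pooling doses over both periods is also uninformative. Over 104 weeks, with full once-daily intake and then half of the twice-daily doses, a switch at Week 26, 52, 78 or 91 gives 104/182 = 57.1%, 104/156 = 66.7%, 104/130 = 80.0% or 104/117 = 88.9%. The SAP's 80% cut is then met or missed according to the switch date.

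**The case against.** **The analyses are already planned.** A reader might infer that the trial has no plan for by-dose or Holter summaries. The documents do not support that: protocol 6.6 pre-specifies them. The SAP names no protocol version after 3, so it may simply predate Version 4, and a later SAP may exist outside the documents supplied. This stands. The gap is in this SAP, which still claims the final analysis.

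**Following protocol 6.6 shrinks the loss.** Selecting within dose removes it for Option 2. The follow-up also has its own column in Appendix 1, apart from unscheduled visits, and 6.6 asks for summaries at each assessment time. This stands in part. SAP 4.6 covers all post-baseline safety assessments and defines no such time point, and within-dose selection still loses Option 1 samples.

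**Twice-daily laboratory data are not lost.** A reader might infer that higher-dose laboratory findings disappear. They do not. Later regular visits carry twice-daily values. Under Option 1 with uniform timing, the record shown instead is a later twice-daily visit for about 54% of patients and a pre-increase one for about 39%. Adverse events and out-of-range listings are unaffected, and the overall shift tables (SAP 4.6.4) possibly so. Investigators review every laboratory result (protocol 4.4.8), and Holter abnormalities are assessed case by case (4.4.9.1). This stands: what is lost is the 4-week time point and the paired change.

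**Compliance is computable under twice-daily dosing.** This is correct. It is not defined at dose level, and the 100% figure rests on one reading of a day under treatment. Diary data, investigator checks and PK samples give other information.

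**Conclusion.** The point holds and should be fixed. The SAP omits three outputs that protocol 6.6 requires for the primary objective. Its selection rule, followed as written, usually leaves the 4-week post-increase laboratory sample out of the by-visit summaries. For Option 2 patients it usually shows a once-daily value in that window, unless selection is made within dose.

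The firm part rests on the stated windows and on attendance within 14 days of target: the visit must be 12 to 14 days early under Option 2, and at most 29 of 182 days qualify under Option 1. The figures of about 93% and 97% assume uniform timing and full attendance. They show size and are not forecasts; missed or systematically early visits lower them. The effect is confined to descriptive by-visit tables, and nothing here shows that a safety signal would go undetected. The compliance item is minor.

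**What to change.** Amend the SAP to protocol Version 4.

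- Make the dose increase visit and the 4-week follow-up separate analysis time points, outside the closest-record rule. Summarize laboratory values there, with the change from before to after the increase, and both Holter recordings.
- Present safety variables by dose at assessment and adverse events by dose at onset, with treatment duration per dose.
- Do not rely on within-dose selection alone, because it still drops a timing-dependent share of Option 1 samples.
- Define compliance as doses taken divided by doses prescribed, from the diary data (protocol 4.2.2.2), shown separately for the once-daily and twice-daily periods.

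The cost is an SAP amendment and programming; no new assessments are needed. The downside is a few more tables, and the extra time points describe only patients who consented to the increase.

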4.6.1 Exposure to Study Medication

The following extent of exposure to study drug will be summarized:

Olesoxime—F. Hoffmann-La Roche Ltd
20/Statistical Analysis Plan BN29854

- Duration of treatment and number of interruption days
- Extent of compliance to the prescribed treatment

The duration of total treatment intake will be calculated from the first day of study medication to the last day of study treatment:

Duration of treatment = date of the last dose – date of the first dose + 1 day

The percentage of compliance over the entire treatment period will be calculated as:

Compliance = total number of days under treatment * 100 / duration of treatment

The number and percentage of patients with overall compliance < 80% and ≥ 80% will be summarized.

4.6.2 Adverse Events

For each adverse event (AE) recorded, the term entered by the investigator describing the event (the 'verbatim term') will be assigned to a standardized term (the 'preferred term') based on the most up-to-date version of MedDRA. Data displays of AEs will be performed using the system organ class and preferred terms. For summaries of AE incidences, patients who experienced the same event on more than one occasion will be counted once in the calculation of the event frequency at the highest intensity reported. Each table will also present the overall number of patients experiencing at least one AE and the total number of AEs reported.

AEs will be summarized for the following analysis periods separately:

Treatment period: includes (a) the AEs for which the onset date is on or after the first day of the study drug up to 28 days after the last dose day; or (b) the AEs for which the onset date is prior to the first dose day with the end date on or after the first dose day or the AE is unresolved, and the most extreme intensity is greater than the initial intensity.

Overall AEs, AEs reported in ≥ 5% of patients, AEs by intensity, AEs leading to death, serious AEs (SAEs), AEs leading to withdrawal of study treatment, AEs leading to dose modification or interruption, AEs related to study treatment (as assigned by the treating investigator), and SAEs related to study treatment will be summarized. SAEs reported in ≥ 1% of patients may also be summarized.

Follow-up period: includes the serious AEs for which the onset date is 29 days or more after the last dose day and that the investigator believes to be related to prior study drug treatment.

In addition, non-treatment emergent AEs, including the SAEs caused by a protocol-mandated intervention (e.g. invasive procedures such as biopsies, discontinuation of

medications) for which the onset date is before the date of the start of study medication, will be listed.

The following rules will be applied for AEs with missing onset and/or end dates:

- Events that are missing both onset and end dates will be considered treatment emergent, given that a patient had at least one dose of study drug.
- If the onset date is missing and the end date is on or after the first dosing date, then the event will be considered treatment emergent.
- If the end date is missing and the onset date is on or after the first dosing date, then the event will be considered treatment emergent.
- If the end date is missing and the extreme intensity is worse than the initial intensity, and the onset date is prior to the first dosing date, then the event will be considered treatment emergent.
- The duration will be set to missing.

4.6.3 Death

A summary table will be generated for the primary causes of death entered in the electronic case report form (eCRF) for each patient who died during the protocol-specified AE reporting period. Patient listings will also be generated containing all details.

4.6.4 Laboratory Data

Results of all laboratory tests collected will be summarized for each time-point using descriptive statistics for the actual values and change from baseline values.

Laboratory data will also be listed for patients with values outside the normal ranges (based on the central laboratory normal ranges), and shift tables to compare the status at baseline to each time-point post-baseline and overall will be presented. In addition, a plot of total bilirubin/upper limit of normal [ULN] versus alanine aminotransferase (ALT)/ULN and aspartate aminotransferase (AST)/ULN at each time-point will be presented.

4.6.5 Vital Signs

Vital signs assessments, including temperature, respiratory rate, pulse rate, blood pressure, weight, height and BMI will be measured throughout the study. If height cannot be measured directly, ulnar length will be used to calculate a surrogate height measure as described in Section 4.3.1. Summaries for vital signs will be presented at each time-point for actual values and change from baseline values. Percentiles for

weight-for-age, stature-for-age, weight-for-stature and BMI-for-age and change from baseline percentiles will also be presented for all patients.

Vital signs data will be listed for patients with values outside the normal ranges for temperature, respiratory rate, pulse rate, systolic blood pressure and diastolic blood pressure. The normal ranges will be based on the age of the patient at the time of the assessment. In addition, shift tables to compare the status at baseline to each time-point post-baseline and overall will be presented. The following normal ranges will be used:

Age (months)	Heart/Pulse Rate (beats/min)	Respiratory Rate (breaths/min)	Systolic Blood Pressure (mmHg)	Diastolic Blood Pressure (mmHg)	Temperature (°C)
>24 and ≤144		18-30	80-125	40-80	35.5-37.8
>144	50-100	12-20	90-140	40-120	36.5-37.5
>72 and ≤96	60-110				
>96 and ≤144	55-100				

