#### **4.4.4 Anthropometric Measurements**

Anthropometric measurements include body weight at every visit, and height at baseline, and every 6 months thereafter *as well as at a possible early discontinuation visit*.

The patient's body weight will be measured to the nearest kilogram using a calibrated scale. For wheelchair-bound patients, weight of the patient will be obtained with a wheelchair balance scale with the patient in the wheelchair. The wheelchair should be also weighed by itself and subtracted from total weight.

The patient's height will be measured or derived *from ulna length* to the nearest centimeter.

Ulna length (from the tip of the olecranon process to that of the styloid process) will be measured using an anthropometer with the patient in sitting position, the left forearm resting comfortably on a table, elbow bent 90 to 110, palm facing downwards and fingers extended but together.

The assessments will be performed as in the Schedule of Assessments [Appendix 1](#), and the formula for calculation of BMI is provided in [Appendix 4](#).

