#### **4.4.14.2      Forced Vital Capacity (FVC)**

Pulmonary Function will be assessed in patients 5 years or older by measuring forced expiratory vital capacity (FVC) (as percent predicted for age and height). Pulmonary measures have been validated in SMA ([Iannaccone et al. 2003](#)). If height cannot be measured (e.g., with scoliosis or contractures), ulna length will be used to calculate a surrogate height measure.

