4.3.1 Demographics

Summary statistics will be presented for the following demographic and baseline characteristics: age (at the time of first treatment in the open-label part of the study), sex, race, ethnicity, country, weight, height, body mass index (BMI) and tanner stage (for patients 9-17 years old).

If height cannot be measured directly (e.g. due to scoliosis or contractures) ulnar length will be used to calculate a surrogate height measure. For patients with an ulnar length measurement available and height indicated as 'derived' in the electronic case report form (eCRF), height will be derived from the measurement of ulnar length using the following formulae:

For patients 5-19 years old (Gauld et al. 2004):

$$\text{Female: height (cm)} = 4.459 * \text{ulnar length (cm)} + 1.315 * \text{age (years)} + 31.485$$

$$\text{Male: height (cm)} = 4.605 * \text{ulnar length (cm)} + 1.308 * \text{age (years)} + 28.003$$

For patients > 19 years old (Elia 2003):

$$\text{Female: height (cm)} = 95.6 + 2.77 * \text{ulnar length (cm)}$$

$$\text{Male: height (cm)} = 79.2 + 3.60 * \text{ulnar length (cm)}$$

Percentiles for weight-for-age, stature-for-age, weight-for-stature and BMI-for-age will also be presented for all patients. These will be based on the Centers for Disease Control and Prevention (CDC) growth standards. For patients > 20 years (240 months) old, percentiles will be based on the reference data for individuals 240 months of age. Percentiles for stature-for-age, weight-for-stature and BMI-for-age may be presented separately for patients whose height can be measured directly and those whose height cannot be measured directly.

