4.4.3 Exploratory Efficacy Endpoints

4.4.3.1 FVC

Pulmonary function will be assessed by measuring forced expiratory vital capacity (FVC; ml). To adjust the FVC according to the height, the age and the gender of patients, the results of the FVC (in liters) will be divided by the theoretical capacity 'TC.' The change from baseline in the FVC/TC (as percent predicted for age and height) and the absolute value will be summarized at each visit using descriptive statistics. The FVC at each visit will also be summarized.

If height cannot be measured directly, ulnar length will be used to calculate a surrogate height measure as described in Section 4.3.1.

The TC is calculated from the following regression equations (Quanjer et al. 1993; Quanjer et al. 1995):

For patients from 3 to 17 years old:

$$\text{Female: } \ln(\text{TC}) = -1.4507 + (1.48 + 0.0127 * A) * H$$

$$\text{Male: } \ln(\text{TC}) = -1.2782 + (1.3731 + 0.0164 * A) * H$$

where H = height (m) and A = age (years) at the assessment visit.

For patients from 18 to 70 years old:

$$\text{Female: } \text{TC} = 4.43 * H - 0.026 * A - 2.89$$

$$\text{Male: } \text{TC} = 5.76 * H - 0.026 * A - 4.34$$

where H = height (m) and A = 25 if age is between 18 and 25 years, otherwise A = age (years) at the assessment visit.

If the height at a visit is missing, the last available measurement will be used to calculate the TC.

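### Change from baseline in height, BMI, stature-based percentiles and FVC/TC is not restricted to pairs of visits that used the same height method

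*SAP*

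**What the plan says.** Protocol 4.4.4 states that the patient's "height will be measured or derived" from ulna length, and schedules "height at baseline, and every 6 months thereafter". Protocol 4.4.14.2 gives the trigger: "If height cannot be measured (e.g., with scoliosis or contractures), ulna length will be used to calculate a surrogate height measure".

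SAP 4.3.1 makes the choice operational. It applies to patients with an ulnar length available and "height indicated as 'derived' in the electronic case report form (eCRF), height will be derived from the measurement of ulnar length", using one pair of formulas for ages 5-19 and another above 19. Nothing in that rule refers to the method used at the patient's baseline.

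SAP 4.6.5 lists height and BMI among the vital signs, repeats the surrogate-height rule ("ulnar length will be used to calculate a surrogate height measure") and adds: "Summaries for vital signs will be presented at each time-point for actual values and change from baseline values". It also presents change in the growth percentiles for all patients. SAP 4.4.3.1 summarises change from baseline in FVC/TC, where TC is a function of height. Its only rule on continuity of height is "If the height at a visit is missing, the last available measurement will be used to calculate the TC", which deals with missing height and not with method.

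**The concern.** A change score is interpretable only if both values come from the same measurement. Here the baseline height can be a direct measurement and a later one the output of a regression on ulna length, or the reverse. The SAP subtracts one from the other. It does not re-derive the baseline, set the pair aside or plan a sensitivity summary.

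A switch is plausible. Scoliosis and contractures are the stated reasons for using the surrogate, and protocol 1.1 lists both as complications of this progressive disease. Follow-up may run to 4 years after the last patient is enrolled. With no control arm and no formal testing, readers will rely on descriptive time courses. A shift in FVC percent predicted or BMI percentile that comes only from a change of method could be read as respiratory or nutritional change.

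The protocol fixes the method elsewhere. Blood pressure uses the same arm and cuff size throughout (4.4.6), and the questionnaire form used at baseline is kept at later visits (4.4.10). Height has no equivalent rule.

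**Working it through.** The plan gives no figure for the difference between measured and derived height, so there is none to reproduce. The check uses the plan's own equations with an assumed difference.

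**Inputs from the documents**
- BMI = weight / height² (protocol Appendix 4).
- TC for ages 3-17 (SAP 4.4.3.1): girls, ln(TC) = -1.4507 + (1.48 + 0.0127·A)·H; boys, ln(TC) = -1.2782 + (1.3731 + 0.0164·A)·H, with H in metres and A in years.
- Ulna formulas (SAP 4.3.1). Ages 5-19: girls 4.459·ulna + 1.315·age + 31.485; boys 4.605·ulna + 1.308·age + 28.003. Above 19: women 95.6 + 2.77·ulna; men 79.2 + 3.60·ulna.

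**Assumptions**
- Derived height exceeds measured height by d = 2, 5 or 10 cm.
- Weight, FVC in litres and age are held fixed, so the true change is zero.
- Heights are 1.35-1.45 m, ages 10-14, and the starting FVC/TC is 60%.

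**Effect of a switch**

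BMI is multiplied by (H/(H+d))². For d = 5 cm this is (1.35/1.40)² = 0.930 and (1.45/1.50)² = 0.934.

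TC is multiplied by exp(k·d), where k is the bracketed coefficient. For girls k is 1.607 at age 10 and 1.658 at age 14; for boys it is 1.537 and 1.603. The ratio does not depend on starting height. For d = 0.05 m it runs from exp(1.537 × 0.05) = 1.080 to exp(1.658 × 0.05) = 1.086, and 60% becomes 60/1.080 = 55.6% to 60/1.086 = 55.2%.

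| d | BMI change | TC rise | FVC/TC of 60% becomes | Shift in points |
|---|---|---|---|---|
| +2 cm | -2.7 to -2.9% | 3.1-3.4% | 58.0-58.2% | -1.8 to -2.0 |
| +5 cm | -6.6 to -7.0% | 8.0-8.6% | 55.2-55.6% | -4.4 to -4.8 |
| +10 cm | -12.5 to -13.3% | 16.6-18.0% | 50.8-51.5% | -8.5 to -9.2 |

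If the derived height is lower, the signs reverse and the shifts are slightly larger. At -5 cm, BMI rises 7.3-7.8% and 60% becomes 64.8-65.2%.

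**One method is not always one formula**

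This matters for the remedy. Applying both ulna formulas to the same ulna at age 19 gives these jumps (formula for above 19 minus formula for ages 5-19):
- Females: +8.7 cm (ulna 18 cm), +5.4 (20), +2.0 (22), -1.4 (24), -4.8 (26).
- Males: +6.2 cm (ulna 20 cm), +4.2 (22), +2.2 (24), +0.2 (26), -1.8 (28).

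A patient who is ulna-derived at every visit can therefore still show an artificial change on crossing the formula boundary.

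**Is it handled elsewhere?**
- SAP 4.3.1 allows three percentiles to be shown separately for patients who can and cannot be measured directly. This is optional, sits under baseline demographics and classifies patients, not visits. It does not cover change in height, BMI or FVC/TC.
- SAP 4.4.4 removes scores after scoliosis surgery or fracture, but for motor function only.

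**What is untouched**

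Weight-for-age, raw FVC, MFM, the natural-history matching and the adverse event analyses do not use height.

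**The case against.** The strongest reply concerns size and direction. The surrogate is meant for patients who cannot be measured directly, so a patient measured at baseline is one whose deformity did not then prevent it. The gap after a switch may be mostly ulna-formula error, which could be small and of either sign. That stands, and it is why 2 cm is in the table and no direction is claimed.

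Frequency is also unknown. The randomised predecessor study enrolled Type 2 and non-ambulatory Type 3 patients, and for those whose baseline samples were analysed, time since last dose was 2.4-4.0 years. Many may already be ulna-derived at baseline and never switch. A reader might infer that switches accumulate with time on drug and produce spurious growth with falling BMI and falling FVC percent predicted. The documents do not support that. They name complications that could prompt a switch, but give no switching rate and no sign for the difference.

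Partial cross-checks exist. Raw FVC is summarised at each visit, and weight is summarised with change from baseline, so a shift in FVC/TC or BMI without a matching shift in litres or kilograms could be noticed. That lowers the stakes but does not correct the change values.

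Finally, two obvious remedies have faults. Imposing ulna-derived height at every visit runs into the formula change at 19. Simply excluding mixed pairs may drop the patients with progressing deformity. Both objections stand and shape the fix. None of this supplies a rule that prevents the mixed subtraction.

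**Conclusion.** The gap is real. As written, the SAP gives a wrong change value in height, BMI, stature-for-age, weight-for-stature, BMI-for-age and FVC/TC for any patient whose height method differs between baseline and visit, unless the two methods happen to agree. Per switching patient, the artefact is about 3%, 7% or 13% of BMI and about 2, 4.5 or 9 points on an FVC/TC of 60%, for assumed differences of 2, 5 or 10 cm at 1.35-1.45 m and ages 10-14.

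The effect on group means cannot be calculated, because the frequency, size and sign of the differences are not documented; a systematic bias in the time trends is not shown. The affected outputs are descriptive safety summaries and one exploratory endpoint. Priority is low to moderate, as a cheap improvement.

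**What to change.** Add to SAP 4.6.5 and 4.4.3.1:
- Flag each baseline-visit pair by height method and by ulna formula, using the existing eCRF field.
- Where ulna length is available at both time-points, compute the change with the same method and the same formula.
- Present change summaries restricted to same-method, same-formula pairs beside the planned all-visit summaries.
- Report the number of mixed pairs at each visit.

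The cost is a short SAP addition, one derivation flag and an extra set of summary rows, with no new patient procedure. The restricted summary will contain fewer patients, because protocol 4.4.4 does not require an ulna length where height was measured directly. Those lost may be the ones with progressing deformity, which is why the all-visit summary stays beside it.
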